## 6.8 Criteria for discontinuation of interventions

The CMT intervention is low risk and therefore we do not anticipate the need to discontinue this treatment because of any harm to participants or worsening of any disease. However, if participants request to discontinue treatment, they will be provided with the option of staying in the trial and returning outcomes or of complete withdrawal from the study.

# 7 PARTICIPANT ELIGIBILITY CRITERIA

The CMT intervention has been positioned as a second-line intervention for people with knee OA which would be offered to NHS patients if they have tried therapeutic exercise and are dissatisfied with the outcome. We will therefore recruit patients with a clinical diagnosis (according to NICE) of knee OA [4] and who have

received NICE-recommended therapeutic exercise but who are dissatisfied with the outcome. The following inclusion/exclusion criteria will be used:

## 7.1 Inclusion criteria

- Over 45 years of age
- Activity-related knee joint pain
- No morning stiffness or morning stiffness that lasts less than 30 minutes
- Score 4 or more (out of 20) on the WOMAC pain scale [19]
- Experienced knee pain for longer than 6 months
- Tried a structured programme of therapeutic exercise and be dissatisfied with the outcome (assessed via screening question). As a minimum, participants must have either seen a healthcare professional and been provided with a structured exercise programme or given access to an NHS exercise App (e.g. getUBetter). The programme could have been undertaken independently or supervised (e.g. an exercise class).
- Able to stand for 5 minutes unaided and walk independently with a maximum of one walking stick/elbow crutch (required to complete the intervention).
- Able to attend for seven hour-long intervention sessions with a physiotherapist

## 7.2 Exclusion criteria

- BMI>33 (as increased subcutaneous fat prevents collection of EMG signals)
- Inflammatory arthritis including rheumatoid arthritis, psoriatic arthritis, ankylosing arthritis, enteropathic arthritis, lupus, septic arthritis or gout.
- Diagnosis of a widespread pain condition, such as fibromyalgia
- Neurological disorder, such as multiple Sclerosis, cerebral palsy or previous stroke (with ongoing neurological deficit)
- Diagnosis of dementia and score >17 on the Telephone-Mini mental state examination (T-MMSE) for cognitive impairment [33]. Note that the T-MMSE (see 'Telephone\_MMSE') will only be collected (via telephone) from participants who have a confirmed medical diagnosis of dementia.
- Unable to speak and understand English sufficiently well enough to receive the intervention

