## LIST OF ABBREVIATIONS

Abbreviation	Explanation
AE	Adverse Event
ANCOVA	Analysis of Covariance
BMI	Body Mass Index
CMT	Cognitive Muscular Therapy
CI	Chief Investigator
DMC	Data Monitoring Committee
DSPT	Data Security & Protection Toolkit
EDI	Equality, Diversity and Inclusion
EMG	Electromyography
EQ-5D-5L	EuroQol 5 Dimensions 5 Levels
FCP	First Contact Practitioner

GAKS	Global Assessment of Knee Symptoms
GCP	Good Clinical Practice
GP	General Practitioner
HES	Hospital Episode Statistics
HRA	Health Research Authority
IRAS	Integrated Research Application System
ISRCTN	International Standard Randomised Controlled Trial Number
ITT	Intention-To-Treat
KL	Kellgren-Lawrence (grading for OA severity)
MMSE	Mini Mental State Examination
MSK CATS	Musculoskeletal Clinical Assessment and Triage Services
NHS	National Health Service
NICE	National Institute for Health and Care Excellence
NIHR	National Institute for Health and Care Research
NJR	National Joint Registry
OA	Osteoarthritis
OARSI	Osteoarthritis Research Society International
OMERACT	Outcome Measures in Rheumatology
PCS	Pain Catastrophizing Scale
PI	Principal Investigator
PPIE	Patient and Public Involvement and Engagement
PSEQ	Pain Self-Efficacy Questionnaire
QALY	Quality-Adjusted Life Year
R&D	Research and Development
REC	Research Ethics Committee
REDCap	Research Electronic Data Capture
RfPB	Research for Patient Benefit
SAE	Serious Adverse Event
SOP	Standard Operating Procedure
TIDieR	Template for Intervention Description and Replication
TMG	Trial Management Group
TSC	Trial Steering Committee

WPAI-OA	Work Productivity and Activity Impairment Questionnaire for Osteoarthritis
WOMAC	Western Ontario and McMaster Universities Osteoarthritis Index

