During the seven hour-long sessions, the physiotherapist works through a clearly delineated protocol which follows the intervention structure described above. Each stage of the protocol allows for tailoring to individual participant needs, e.g. psychological factors/different learning styles. Between each clinical session, participants are given 3-4 specific 'challenges' which require them to improve awareness of muscle tone, improve their capacity to relax the quadriceps muscles and change their psychological responses to pain. After each session, the participant is provided with a summary sheet which lists learning points and summarizes each challenge. To facilitate this learning/practice, participants are provided with access to an online platform which includes both written documents and animated videos. If participants are unable to engage with the online platform (e.g. no access to the internet), they are provided with a paper booklet. Following completion of the treatment, the aim is that the new muscle coordination patterns become habit. Therefore, while participants are encouraged to continue to practice the different challenges, the primary aim is that they have skills and knowledge to self-manage their knee OA, including any pain flare ups, as they go about their daily life.

Risk assessment:

This CMT intervention is very low risk. To date, we have delivered implementations of the CMT intervention to over 200 participants with no adverse events. Nevertheless, we have created a risk assessment (see 'CMT for musculoskeletal conditions - risk assessment') which will be used as part of the training that the CMT physiotherapists receive (see sections below). This includes standard precautions in rehabilitation, such as minimising infection risk, checking equipment regularly and ensuring there are no hazards which could cause a trip or fall. In addition, the physiotherapist will monitor for any allergic skin reaction to the EMG sensors and monitor for any dizziness which may result from inappropriate practice of the CMT breathing exercises.

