## 8.3 Consent

All participants will have the opportunity to read the participant information sheet before they reach out to the local team or research team. Full screening will be undertaken via telephone call by the research team and may be undertaken by phone or face-to-face by the local team. Once deemed eligible, participants will have the

opportunity to ask for clarification on any aspects of study participation, trial processes or any issues related to personal circumstances. The recruiter will then read through the consent form with the participant and ensure understanding. The participant will either initial the boxes and sign the consent form (if face-to-face) or be sent a copy of the consent form in the post (see 'Consent form cover letter') and asked to initial all the boxes and sign (if telephone). They will also be asked to complete the data access form (see section on Baseline data below) at the point of consent. The GCP trained staff member who carries out the consenting process countersigns the consent form indicating all available information has been given to the participant. The consent form and data access forms are then returned to the University/local site either via a scan/photo or via pre-paid postage envelope.

It will be the responsibility of the local site Principal Investigator (PI) to ensure that all staff who take consent are appropriately trained and on the delegation log for the study. Informed consent must be obtained prior to the participant undergoing procedures that are specifically for the purposes of the study.

Reasons for declining participation, where given, will be recorded on the screening log.

For participants who are eligible, the research team or local team will record the following details:

1. Name
2. Date of birth
3. Contact telephone number
4. Email address
5. Home address
6. GP practice
7. NHS number (if known)
8. Any preference for physiotherapy appointment times.

Once the consent form (see 'Consent form (Clinical trial)') and data access (see 'Data Access Form') form have been received, the participant will be formally enrolled onto the study. With the participants' permission, the research team will then send a letter to the GP (see 'Letter to GP') informing the GP of the participants' participation in the study. If participants do not return the consent from within the specified period (see Section 7.8), all personal data (listed above) will be deleted.

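### The dementia exclusion appears to be reversed: it removes people with dementia who score above 17 on the T-MMSE and does not exclude those who score 17 or below

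*Protocol*

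**What the plan says.** The line stands in the protocol under "7.2 Exclusion criteria", so a person who meets it is kept out. It reads "Diagnosis of dementia and score >17 on the Telephone-Mini mental state examination (T-MMSE) for cognitive impairment". A note attached to it says that the T-MMSE "will only be collected (via telephone) from participants who have a confirmed medical diagnosis of dementia".

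The only other entry in that list about a candidate's ability to take in the treatment is "Unable to speak and understand English sufficiently well enough to receive the intervention", which concerns language. The List of Abbreviations expands MMSE as "Mini Mental State Examination". It says nothing about how the test is scored, and neither does any other part of the protocol. The cut-off appears nowhere else, and the single amendment listed in Appendix 1 does not concern it.

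**The concern.** A second-step test in people who already have a dementia diagnosis has one plausible purpose: to separate those too impaired to take part from those who can. On an instrument where more points mean better cognition, excluding scores above a threshold does the reverse. It turns away people with better-preserved cognition and does not stop those with poorer cognition.

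Three things are at stake.

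- **Consent.** This is the only cognitive screen listed ahead of a consent process that may take place by telephone (Section 8.3).
- **The intervention.** Between sessions participants carry out tasks meant to "improve awareness of muscle tone, improve their capacity to relax the quadriceps muscles and change their psychological responses to pain" (Section 6.2), which require learning, reflection and recall.
- **Fair access.** People with dementia who could take part would be refused.

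Screeners cannot simply correct the line in practice. Section 8.1 has local and University teams apply the listed criteria, and Section 13.6 does not allow planned deviations or waivers.

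**Working it through.** No sample-size or power arithmetic applies. The check is a logical one.

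**Inputs**

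1. Type of criterion: exclusion (Section 7.2).
2. Rule: dementia diagnosis AND T-MMSE score > 17 leads to exclusion (Section 7.2).
3. Who is tested: only people with a confirmed dementia diagnosis (note in Section 7.2).
4. Scoring direction: a higher score means better cognition. This is an assumption, being the ordinary direction of the named instrument; the protocol does not print it.

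**Step 1: the conjunction.** Could the line mean two separate exclusions, dementia or a score above 17? The note on who is tested rules this out. If dementia alone excluded a person, testing only people with dementia would decide nothing. The two conditions must be read together, and among people with dementia the score alone decides.

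**Step 2: the rule as written, beside the two simplest reversals.**

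| Dementia diagnosis | T-MMSE score | As written (> 17) | Reversed, 17 excluded (≤ 17) | Reversed, 17 not excluded (< 17) |
|---|---|---|---|---|
| No | not tested | not excluded | not excluded | not excluded |
| Yes | 10 | not excluded | excluded | excluded |
| Yes | 17 | not excluded | excluded | not excluded |
| Yes | 18 | excluded | not excluded | not excluded |
| Yes | 24 | excluded | not excluded | not excluded |

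*Not excluded* means not excluded by this criterion; all the others still apply. The last two columns only show what changing the direction does. They do not propose a cut-off.

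**Step 3: direction.** Under input 4, the as-written column removes the less impaired (18, 24) and leaves the more impaired (10, 17). If the form were instead scored so that a higher number means worse cognition, the same column would be sensible and there would be no error. The finding therefore rests on input 4.

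**Step 4: is it corrected elsewhere?** No. Sections 8.1 and 8.3 refer back to the eligibility criteria and do not restate the threshold.

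**Step 5: effect on the design figures.** None. The target of 126 per group in Section 10.1 uses no input from this line.

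**The case against.** The strongest objection is that the decisive premise is not in the protocol. The direction of the scale is not printed, the Telephone_MMSE form is not shown, and the reference to cognitive impairment describes what the test is for, not which side of 17 should be excluded. This stands to the extent that the direction must be declared as an assumption. It does not remove the point, because nothing in the protocol suggests that the form is scored opposite to the instrument it is named after.

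The second objection concerns harm. A reader might infer that sites would go on to consent and randomise the most impaired candidates. The protocol does not support that. Failing to meet one exclusion is not admission. Section 8.3 provides that "The recruiter will then read through the consent form with the participant and ensure understanding", with countersignature by GCP-trained staff, and requires informed consent before any study procedure. Record searches are made by the direct care team (Section 8.1). Candidates must also return the consent and data access forms and the baseline questionnaires before randomisation (Sections 8.3, 8.4 and 8.7). Someone unable to understand the study would probably be stopped at one of these steps. Section 8.3 contains no error; it is a safeguard. It does not, however, describe a specific capacity assessment, so it does not replace a cognitive screen that works.

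A reader might also infer that the rule misclassifies every screened person with dementia. That would follow only if the intended rule were the exact complement at 17. With the boundary and the cut-off still to be confirmed, some people would have the same status under either version, as the row for a score of 17 shows.

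**Conclusion.** The point holds on one stated assumption, that a higher T-MMSE score means better cognition. On that basis Section 7.2 excludes people with dementia and better-preserved cognition, and does not exclude those scoring 17 or below. The line is best seen as a probable drafting slip in a single inequality sign, not a deliberate design choice.

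Only candidates with a dementia diagnosis are affected. The protocol gives no count, but they are likely to be few. A wrongly admitted person would remain in the primary analysis, because Section 10.4 analyses everyone as randomised. Even so, a reader should not conclude that the 12-month WOMAC comparison is compromised: with few people affected and 1:1 allocation stratified by site, the effect on the treatment estimate is probably negligible. The correction is still necessary, on grounds of participant protection and eligibility integrity. Power and bias are not the reason.

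**What to change.** Check how the Telephone_MMSE form is scored. Then bring the inequality in Section 7.2 into line with it and with the screening forms, so that the criterion excludes people whose score indicates impairment. The clinical team should confirm the cut-off and say whether a person scoring exactly at it is in or out; this review takes no position on either. Adding the scoring direction to the criterion would let screeners see which way it runs.

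The cost is a one-line amendment, matching edits to any screening form that repeats the line, and a check of anyone already screened under it (the Trial Summary plans recruitment from 1 November 2025). The sample size and the analysis do not change.

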# 8 TRIAL PROCEDURES

## 8.1 Participant identification and screening

We propose identifying potential participants via five mechanisms:

1. Through NHS musculoskeletal physiotherapy departments
2. Through NHS musculoskeletal assessment and triage/treatment services (MSK CATS)
3. Through GP practices and First Contact Practitioners (FCPs)
4. Via Social media advert, the University of Salford Hub advert and posters

5. Through a database of volunteers held at the University of Salford

*1 NHS physiotherapy departments – research site*

NHS physiotherapy departments will be set up as research sites with local staff undertaking screening and consenting activity. In situations where local staff have limited capacity for recruiting and consenting, then research staff (at the University of Salford) will screen and consent participants. However, research staff at the University will not have direct access to patient information and will carry out full screening only after the participant has independently contacted the University or has provided consent to contact. With this approach, initial searching of NHS patient records/patient identification will always be undertaken by the patient's direct care team with full screening undertaken by either local site staff or University of Salford staff.

Potential participants in physiotherapy departments will be identified through searching of electronic records or during routine clinical consultation. This consultation will include individual treatment sessions, during group exercise classes or at the point of discharge from NHS clinical services. Electronic searching will be carried out by direct healthcare team members to identify people with a relevant diagnostic (SNOMED CT) code for knee OA. The resulting patient lists will then be screened to rule out patients who do not meet eligibility criteria. Eligible participants will then be sent an invitation letter (see 'Letter of invitation') and participant information sheet (see 'Participant information sheet (Clinical trial)') and asked to contact the local team. The local team may choose to follow-up the initial invitations with a phone call or send a reminder. Participants who contact the local team will undergo full screening following local procedures.

If local staff do not have the capacity to undertake full screening and consent, then participants will be instructed to contact the University research team. In this situation, participants identified after the initial search will be sent either the participant information sheet (and letter of invitation) or send a text message invitation to participate (see 'Text Invitation'). The text message contains a link to a webpage which provides an overview of the study. Similarly, the participant information sheet also contains the link along with QR code for this web page. Note that this page (<https://hub.salford.ac.uk/volunteer-for-research/studies/bepko-3-trial/>) which will ultimately contain a link to the participant information sheet. Embedded within the webpage will be a link to an online form which volunteers will complete if they are interested in taking part. The questions from this form have been copied to the document 'Web screening form'. All data submitted via these forms is strictly confidential and held on a secure server at the University of Salford. If participants do not want to complete an online form, they are still free to contact the research team directly if they would prefer to be screened over the phone. With either of these two approaches, the research team will not have access to patient records. However, in some cases, patients may learn about the study from NHS staff (direct care team) and may be happy for their contact details to be passed directly to the research team at the University of Salford. In this situation, participants will complete a consent to contact form (see 'Consent to contact form'). A contact email/phone number will then be passed to the research team via secure NHS email. This will allow the research team to contact the participant directly to undertake a full screening.

*2 Musculoskeletal triage services (MSK CATS) – Participant identification centre*

NHS patients with knee OA are typically referred to MSK CATS service from their GP once they have tried, but are dissatisfied with the outcome of therapeutic exercise. This triage service is the gateway for onward referral onto orthopaedic management of chronic knee pain. We will use these services as participant identification centres, identifying MSK CATS service within close proximity of each research delivery sites. We will use the

same approach for participant identification and screening as described for NHS physiotherapy services, either at the point of clinical consultation or by screening electronic records and sending text message invitations or letters of invitation. If the local team does not have capacity to screen and consent, then the research team will undertake these activities. The research team will not have access to patient records but will receive details of the number of invitations sent by each MSK CATs team.

### *3 GP practices – Participant identification centre*

We will identify GP practices within close proximity of each of the research delivery sites to act as participant identification centres. We will follow the same procedure as outlined above, identifying participants through electronic searching patient records diagnostic (SNOMED CT) code for consultation for knee OA within the last 48 months. Following screening of the list of people identified through the search (by a member of the direct care team), invitations will be sent via letter or text message. Full screening and consenting will be undertaken by research staff at the University of Salford once participants independently make contact with the research team. We note that the research team will not have access to patient records but will receive details of the number of invitations sent by each GP.

### *4 Social media advert, University of Salford Hub advert and poster*

We will use social media channels, such as Twitter (X), Facebook, and Instagram to promote the study (see 'Social media advert'). We will also use the University of staff internal hub (web page) to promote the study (see 'Hub advert'). Individuals who are interested in participating in our research will be directed to the webpage described above. We will also place poster advertisements (see 'Poster') around the University of Salford and within NHS sites, such as GP practices or physiotherapy departments. We will also put the poster in community sites, such as churches/mosques and shopping centres. The poster contains a QR code, which links to the webpage described above. We will ensure that we have appropriate permissions before placing posters in community settings, e.g. from church officials. With this approach, full screening and consenting will be undertaken by research staff at the University of Salford.

### *5 University of Salford database – Participant identification centre*

At the University of Salford, we hold a database of people interested in knee OA research. People registered on these databases who live within 30 minutes travel of one of the research sites will be sent the participant information sheet and the invitation letter or sent a text/link to the webpage, described above. With this approach, full screening and consenting will be undertaken by research staff at the University of Salford.

